### **1.2 Secondary Objectives**

- To confirm our previous finding that the COMT val158met polymorphism is associated with placebo response.
- To replicate our previous finding that certain personality traits (extraversion, agreeableness, openness) are associated with the placebo response in IBS.
- Using ethnographic interviews to obtain insight into patients' experiences, including their views of the clinical encounter.
- An exploratory objective of the study is to obtain pilot data to assess whether double-blind peppermint oil results in greater clinical improvement compared to double-blind placebo in patients with IBS.

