### **8.2 Stratification**

Stratification will be based on IBS symptom severity score (< 300 and ≥ 300) and gender, resulting in 4 strata. Each stratum will have a different color randomization envelope and a unique set of randomization ID numbers.

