### 8.3 Analyses

All tests will be two-tailed with  $\alpha=.05$ . For our primary analyses, we will use a modified intention-to-treat analysis including any patient who was randomized and provided a baseline assessment and at least one post-baseline primary outcome assessment. We will also run per protocol analyses, and any substantive differences between the two methods will be reported.

We will examine the amount of missing data and the nature of the missingness (missing completely at random, missing at random, and missing not a random). If necessary, we will conduct a full intention to treat analysis.

**Aim 1.** To determine whether 6 weeks of open-label placebo, double-blind placebo and no-treatment results in different clinical outcomes. To test this aim, we will conduct a one-way analysis of covariance. In addition to treatment group, the model will include baseline IBS-SSS and stratification factors for gender and symptom severity.

Assuming that there is a significant difference between the 3 groups, Dunnett's analysis will be used to do pairwise analyses of the following aims

**1a.** To determine if 6 weeks of open-label placebo results in superior clinical outcome than no treatment control. Hypothesis: open-label placebo > no treatment control.

**1b.** To determine if 6 weeks of open-label placebo results in superior clinical outcome than double blind placebo. Hypothesis: open-label placebo > double-blind placebo.

**Secondary Aims Analysis Plan:** There are three secondary multi-disciplinary aims in this study.

**Secondary Aim 1 (Genetics Aim):** In our previous large RCT we found that the number methionine alleles in COMT val158met was associated with placebo responses especially to a combined placebo and supportive patient-provider relationship. We plan to confirm these findings and extend them by evaluating additional candidate genes implicated in placebo. Exploratory analyses will be performed in other candidate genes associated with placebo including: the mu-opioid receptor polymorphism (OPRM1 A118G), FAAH polymorphisms Pro129Thr. monoamine oxidase gene polymorphisms, and serotonin-related polymorphism CGTTLPR and G-703T (polymorphism in the tryptophan hydroxylase-2 (TPH-2) gene promoter).

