DNA will be extracted from those study participants who agree to the genetic screening and will be analyzed by a TaqMan allele discrimination assay. Subsequently, COMT and other candidate genotypes will be correlated with response to placebo or active drug treatment using the above mentioned outcomes. Furthermore, potential correlations of the COMT and other genotypes and patient-disease characteristics, for instance pain experience at baseline, will be examined.

**Secondary Aim 2 (Psychological Aim):** In our previous large RCT in IBS we found that higher levels of extraversion, agreeableness, and openness to experience are associated with increased response to placebo treatment, especially with an augmented patient-practitioner relationship. We will use the Five Factor Inventory (FFI) to measure these personality traits and

then use multiple regression to examine their association with outcomes after controlling for baseline severity.

**Secondary (exploratory) Aim:** To determine if 6 weeks of double-blind peppermint oil results in greater improvement than double-blind placebo in patients with IBS. Hypothesis: Double-blind peppermint oil > Double-blind placebo. To test this aim, we will conduct an analysis of covariance. In addition to treatment group, the model will include baseline IBS-SSS and stratification factors for gender and symptom severity.

**8.4 Power Calculations:** To estimate the effect size for Aim 1, we used our previous pilot trial in IBS. In that study, the effect size for the difference between open-label placebo and no-treatment on the IBS Symptom Severity Scale was  $d=0.53$ . For this comparison, there will be 88 patients in each group, and using ANCOVA to control for baseline scores leaves the power for the 3 group comparison at .96. To estimate the power for secondary (exploratory) aim using ANCOVA to control baseline scores leaves the power of .60; however, using more recent data that suggest an effect size of  $d=0.50$ , the power would be .78.

**8.5 Missing Data Minimization Strategies:** Missing data minimization strategies includes patient retention efforts and a modified intent-to-treat analysis. Each individual patient reported assessment will be captured electronically at each visit with missing responses prohibited by the electronic system.

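### Minor, nearly free improvement: add gender (and treatment group where arms are pooled) to the Secondary Aim 2 personality regression, which now adjusts only for baseline severity

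*Combined protocol and SAP*

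**What the plan says.** Section 1.2 sets the objective: "To replicate our previous finding that certain personality traits (extraversion, agreeableness, openness) are associated with the placebo response in IBS". Section 8.3, Secondary Aim 2, gives the analysis: measure the traits with the Five Factor Inventory and "then use multiple regression to examine their association with outcomes after controlling for baseline severity". Baseline severity is the only covariate named. The sentence does not say which arms enter or whether treatment group is a term.

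Section 8.2 stratifies the randomisation on IBS-SSS, split at 300, "and gender, resulting in 4 strata". In section 8.3, the Aim 1 ANCOVA and the exploratory peppermint oil ANCOVA are both specified in the same words: "In addition to treatment group, the model will include baseline IBS-SSS and stratification factors for gender and symptom severity". Nothing elsewhere adds gender to the personality regression.

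**The concern.** In the randomised comparisons, stratified allocation already balances gender across arms, and the gender term there mainly adds precision. Personality traits are observed, not assigned. Stratifying on gender does nothing about a correlation between gender and a trait within an arm, so in this regression only the model can deal with it.

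The aim is to replicate a named result. If a trait association is reported, a reader will ask whether it only reflects a difference between men and women, and the plan has no pre-specified answer. Adding gender after seeing the data would be a post hoc choice. The bias can go either way: it can suggest a trait effect where there is none, or mask a real one if the signs oppose.

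**Working it through.** The plan gives no sample size, power or error rate for Secondary Aim 2, so there is no figure of its own to reproduce.

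**Inputs from the documents.** Two-sided alpha is .05 (8.3). There are 88 patients in each large arm (8.4), so the two placebo arms give 2 × 88 = 176 and the three main arms give 3 × 88 = 264. The plan does not say which of these applies.

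**Assumed inputs, none from the documents.** The share of women *p* is 0.7 or 0.8. The gender difference in the trait is *dt*, and the gender difference in the outcome after baseline adjustment is *dg*, both in within-gender SD units. The true trait effect given gender is zero.

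**Method.** With *q* = 1 − *p*:

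- Convert each difference to a correlation: r(d) = d√(pq) / √(1 + d²pq).
- Correlation induced between trait and outcome: r = r(dt) × r(dg).
- Shift of the test statistic: z = r√(n − 3).
- Rejection rate: P(|Z + z| > 1.96).

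**Worked case.** Take dt = 0.6, dg = 0.4, p = 0.7, n = 176, so pq = 0.21.

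- r(dt) = 0.6 × 0.458 / √1.0756 = 0.265
- r(dg) = 0.4 × 0.458 / √1.0336 = 0.180
- r = 0.265 × 0.180 = 0.048
- z = 0.048 × √173 = 0.63
- Rejection rate = P(Z > 1.33) + P(Z < −2.59) = 0.0915 + 0.0048 = 9.6%

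**Results over the range** (lower value at 80% women, upper at 70%):

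| Trait / outcome difference (SD) | Induced r | Rate, n = 176 | Rate, n = 264 |
|---|---|---|---|
| 0.2 / 0.2 | .006-.008 | 5.1% | 5.1-5.2% |
| 0.4 / 0.3 | .019-.025 | 5.7-6.2% | 6.1-6.8% |
| 0.6 / 0.4 | .037-.048 | 7.7-9.6% | 9.2-12.1% |

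If either difference is zero, the rate is 5.0%.

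**Cross-check by another method.** A noncentral t calculation with 50% or 75% women gives, for 0.4 SD in trait and 0.3 SD in outcome, 6.0-6.7% at n = 176 and 6.5-7.6% at n = 264. With 0.5 SD in both it gives 9.1-12.2% and 11.2-15.9%. If all four arms were pooled (88 × 3.5 = 308 patients), the 0.5/0.5 case reaches 12.3-17.8%. The induced correlation is never above about .06.

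**Effect of the fix.** Simulation with 4,000 runs per case, 75% women and a baseline covariate in the model:

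| Trait / outcome (SD), n | Without gender | With gender |
|---|---|---|
| 0.4 / 0.3, 176 | 5.5% | 5.1% |
| 0.5 / 0.5, 176 | 9.2% | 5.0% |
| 0.5 / 0.5, 264 | 10.9% | 4.6% |

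All rates are per trait, and three traits are named. The calculations take one trait at a time. If the traits enter the regression together, the gender difference that counts is the one left in a trait after the others are adjusted for.

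**The case against.** The strongest reply is that the plan promises only an association. Section 1.2 says "certain personality traits (extraversion, agreeableness, openness) are associated with the placebo response in IBS", and section 8.3 makes no claim that the effect is causal or independent of gender. A trait that tracks gender may truly be associated with outcome, and a false positive exists only against a gender-independent target. This stands, so the rates above are stated for that target alone.

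The harm also needs two links that the documents do not supply: gender with the trait, and gender with the outcome after baseline adjustment. A raw gender difference in Week 6 scores would not be enough, because baseline severity is already in the model. This stands too. A reader might infer from the stratification that the sponsor has shown gender to be prognostic, but section 8.2 gives no reason for the choice.

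The covariates of the earlier trial's model are not given, so a gender-adjusted model could differ from the one being replicated. This is a fair point, and the fix answers it by keeping both models.

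A reader might also infer that the plan contradicts itself by adjusting for gender in one place and not in another. The documents do not support that. Carrying stratification factors into the randomised comparisons is ordinary practice, and the reason does not transfer to a trait regression. The genetics analysis names no covariates either: "COMT and other candidate genotypes will be correlated with response to placebo or active drug treatment".

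Finally, the same sentence leaves out the arms and any treatment term, arguably a larger gap given that the objective concerns placebo response. This is true. It does not remove the case for gender, and the fix below covers the treatment term.

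**Conclusion.** The point holds as a minor improvement. The regression names one covariate. Gender is already known for every randomised patient, and in a non-randomised comparison adjustment is the only protection against confounding by it.

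The size depends wholly on assumed gender differences. For a gender-independent trait effect, the per-trait false-positive rate is about 5% at 0.2/0.2 SD, 6-7% at 0.4/0.3 SD and 8-12% at 0.6/0.4 SD (trait/outcome), with 176 to 264 patients and 70-80% women. The higher rates in the cross-check need 0.5 SD in both.

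The documents do not support the stronger conclusion that the regression as written will report a gender difference as a replicated personality effect. They give no gender mix, no gender difference in trait scores and no gender effect on IBS-SSS.

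**What to change.** In section 8.3, Secondary Aim 2, replace the closing phrase that names baseline severity as the only control with: adjusting for baseline IBS-SSS, the stratification factors (gender and symptom severity) and, where more than one arm is included, treatment group. Add that the model adjusted for baseline severity only will also be reported, so that the result can be set beside the earlier trial.

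This matches the covariates of the Aim 1 ANCOVA, including its treatment term. The cost is a few degrees of freedom and one extra model. No new data are needed, because gender must be known before a patient can be assigned to a stratum.

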## **1. Study Objectives**

### **1.1 Primary Objectives**

The primary objectives of this study are to: (1) to determine whether 6 weeks of open-label placebo, double-blind placebo and no additional treatment control results in different clinical outcomes in patients with IBS and (2) assuming there are significant differences (a) to determine whether open-label placebo results in greater clinical improvement compared to no additional treatment control and (b) to determine if open-label placebo results in greater clinical outcome than double blind placebo.

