### 3. Study Design

#### 3.1 Overall Design and Plan of the Study

This study aims to investigate the effects of open-label placebos with double-blind placebos as administered in a randomized controlled trial in a 6-week trial with 313 IBS patients on standard treatment for IBS randomly assigned to one of four arms:

- open-label placebo
- double-blind placebo
- double-blind peppermint oil
- no additional treatment control.

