#### **4. Selection and Enrollment of Participants**

Approximately 313 IBS patients who meet all of the inclusion criteria and none of the exclusion criteria will be enrolled.

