### **5. Study Interventions**

#### **5.1 Interventions, Administration, and Duration**

The study involves four groups as follows:

- open-label placebo 1 softgel TID (N~80)
- double-blind placebo 1 softgel TID (N~80)
- double-blind peppermint oil 1 softgel TID (N~40)
- no additional treatment control (N~80)

Placebo will be supplied as soybean oil (manufactured by SoftGel Technologies Inc.), matched to peppermint oil softgels (Pepogest™). The open-label and double-blind placebo are identical and both are matched to the peppermint oil. Each peppermint oil dose is 0.2mL. Study drug should be administered approximately 30 minutes before meal times.

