## **8. Statistical Considerations**

### **8.1 Randomization**

Treatment assignments will be generated using permuted block randomization with randomly varying block sizes. Randomization will be done in a 2:2:2:1: ratio (open-label placebo; double-blind placebo; no treatment control; double blind peppermint oil). Randomization for the qualitative sub-study will be done. Randomized assignments to one of the four groups will be sealed in sequentially numbered opaque envelopes.

A random subset of approximately 57 of the participants will be selected for participation in the nested qualitative study. The participants will be randomly selected in the same ratio as the primary randomization. Care providers will be blinded to participation in the sub study. A list of selected randomization IDs and access to the REDCap patient scheduling module will be provided to the interviewer so that he or she can conduct the qualitative interview after the participant has completed the final clinical evaluation.

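### Section 5.1's arm sizes sum to about 280, which contradicts the 313 of Sections 3.1 and 4 and the 88 per group on which Section 8.4's powers rest

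*Combined protocol and SAP*

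**What the plan says.** Total sample size. Section 3.1 describes the study as "in a 6-week trial with 313 IBS patients on standard treatment for IBS", and Section 4 repeats it: "Approximately 313 IBS patients who meet all of the inclusion criteria and none of the exclusion criteria will be enrolled".

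Allocation. Section 8.1: "Randomization will be done in a 2:2:2:1: ratio", with peppermint oil as the smaller arm.

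Arm sizes. Section 5.1 gives approximate sizes arm by arm: "double-blind placebo 1 softgel TID (N~80") and "double-blind peppermint oil 1 softgel TID (N~40"), with about 80 also for open-label placebo and about 80 for no additional treatment.

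Power. Section 8.4 takes d=0.53 for open-label placebo against no treatment from a pilot trial and continues: "88 patients in each group, and using ANCOVA to control for baseline scores leaves the power for the 3 group comparison at .96". For the exploratory peppermint oil aim it gives .60, and .78 at d=0.50.

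Primary pairwise aims. Section 1.1 includes, as objective 2(b), "to determine if open-label placebo results in greater clinical outcome than double blind placebo". Section 8.3 makes this aim 1b, tested after a significant 3-group result, when Dunnett's "analysis will be used to do pairwise analyses of the following aims". Section 8.4 gives no separate effect size or power for it.

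**The concern.** The plan has two different sample sizes. A reader who starts from Section 5.1 expects 280 patients; one who starts from Section 3.1, 4 or 8.4 expects 308 to 313. The document does not say whether any of these counts is randomised or evaluable, so the reader cannot tell whether Section 5.1 is a slip or an unlabelled target after losses. If 80 and 40 were the numbers analysed, the powers in Section 8.4 would be computed on more patients than the analysis would have.

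A smaller matter sits beside this. Section 8.4 quotes one power for Aim 1, and a reader could take it to cover both primary pairwise aims.

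**Working it through.** **1. Counts**

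- Section 5.1: 80 + 80 + 40 + 80 = 280.
- Sections 3.1 and 4 with Section 8.1: 313 × 2/7 = 89.4 per large arm; 313 × 1/7 = 44.7 on peppermint oil.
- Section 8.4: 88 per large arm implies 44 on peppermint oil at 2:1, so 3 × 88 + 44 = 308.
- Gap: 313 − 280 = 33; 33/313 = 10.5%.

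Sections 3.1, 4, 8.1 and 8.4 agree to within rounding. Section 5.1 does not.

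**2. Inputs for power**

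From the documents: two-sided alpha .05 (Section 8.3); d=0.53, 88 per group and d=0.50 (Section 8.4). Assumed, because not stated: the correlation r between baseline and outcome, and the double-blind placebo mean. The models use one covariate.

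**3. The 3-group test (noncentral F)**

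Noncentrality = n × Σ(group mean − grand mean)² / (1 − r²), with 2 and 3n − 4 degrees of freedom. With means .53, 0, 0 (double-blind placebo equal to no treatment), the sum of squares is 0.53² × 2/3 = 0.1873. Means .53, .53, 0 (double-blind equal to open-label placebo) give the same sum.

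| n per group | r | Noncentrality | Power |
|---|---|---|---|
| 88 | 0 | 16.48 | .960 |
| 88 | .15 | 16.86 | .964 |
| 80 | 0 | 14.98 | .941 |
| 80 | .15 | 15.33 | .946 |

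The plan's .96 reproduces at 88. It depends on the unstated mean: with double-blind placebo halfway (.265), 88 per group gives .889 at r=0 and .896 at r=.15.

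**4. Peppermint oil against double-blind placebo at d=0.50 (noncentral t)**

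Noncentrality = d × √(n1 × n2/(n1 + n2)) / √(1 − r²), with n1 + n2 − 3 degrees of freedom.

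| Sizes | r | Noncentrality | Power |
|---|---|---|---|
| 88 and 44 | 0 | 2.708 | .767 |
| 88 and 44 | .15 | 2.739 | .776 |
| 80 and 40 | 0 | 2.582 | .726 |
| 80 and 40 | .15 | 2.612 | .736 |

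The plan's .78 reproduces with 88 and 44 at r of about .15 to .2 (.783 at r=.2). At r=.5 it would be .874, so a correlation that high does not fit the plan's own figure. The .60 has no effect size attached and was not recomputed.

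**5. Secondary note: aim 1b**

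Step 3 shows that the 3-group power is the same whether double-blind placebo equals no treatment (1b difference 0.53 SD) or equals open-label placebo (1b difference zero). The .96 therefore carries no information about 1b.

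Power for 1b was simulated as a significant 3-group test followed by Dunnett's test (critical values 2.224 at 88 and 2.225 at 80), assuming r=.15 and an open-label versus no-treatment difference of 0.53 SD:

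| Open-label minus double-blind, SD | 88 per group | 80 per group |
|---|---|---|
| 0.53 | .90 | .87 |
| 0.40 | .67 | .63 |
| Detectable at 80% power | 0.46 | 0.48 |

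**The case against.** **The sizes in Section 5.1 are marked approximate, and no analysis uses them.** The second part stands: Section 8.4 uses 88, so this is a correction of text and not a flaw in the design. The first does not: approximation does not explain 33 patients.

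**The 80s and 40 may be expected completers.** That is possible, since a 10.5% loss from 313 leaves 280. But the text does not say so, and 88 would then not be the number analysed.

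**The recalculation alone cannot show which sizes were used, because r is unstated.** This is fair. With 80 and 40, r between .3 and .4 gives a 3-group power of .959 to .972 and a peppermint power of .766 to .798, close to the stated values. The attribution of .96 to 88 rests on Section 8.4 saying 88. At any fixed r, 80 and 40 still give less power than 88 and 44.

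**A reader might infer that the plan tolerates a loss of only 5 patients (313 − 308, 1.6%).** The documents do not support that. No section presents the difference as a dropout allowance, 313 is approximate in Section 4, and 88 is not labelled randomised or evaluable. The modified intention-to-treat set needs only one post-baseline score, Section 8.3 allows a full intention-to-treat analysis if necessary, and Sections 6.2.5 and 8.5 plan data collection and retention. An attrition figure is absent, but that is an omission.

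**A reader might also infer that aim 1b is underpowered or that .96 is wrong.** Neither follows. The .96 is described as the power of the 3-group comparison and reproduces as such. Section 2.1 says no earlier study had compared the two kinds of placebo, so there was no estimate to use for 1b. If double-blind placebo were equal to no treatment, which fits .96 at low r and the direction of hypothesis 1b, power for 1b would be about .90.

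**Conclusion.** The arm sizes in Section 5.1 are inconsistent with the rest of the plan: 280 against 313, a shortfall of 33 patients or 10.5%. This is certain from the counts and needs no assumption.

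The consequence for power is modest. With r between 0 and .15 (assumed) and the double-blind placebo mean equal to one of the other two arms, Section 5.1's sizes would lower the 3-group power from .96 to about .94-.95. The exploratory peppermint power at d=0.50 would fall from .78 to about .73-.74. The primary test stays well powered under those assumptions.

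The observation on aim 1b is a reporting note and not an error. The .96 is correct for what it describes, but it should not be read as the power of open-label against double-blind placebo.

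**What to change.** Correct Section 5.1 to about 89 randomised in each of the open-label placebo, double-blind placebo and no-treatment arms and about 45 on peppermint oil, total 313. Alternatively, if about 80 and 40 are the evaluable targets, label them so, state the roughly 10.5% loss that this implies, and restate the Section 8.4 powers at those numbers. Either way, label each count in Sections 3.1, 4, 5.1 and 8.4 as randomised or evaluable.

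Optionally, in Section 8.4, state the assumed baseline correlation and double-blind placebo mean, and add a detectable difference for aim 1b: about 0.46 SD at 88 per group or 0.48 SD at 80, on the assumptions given with the calculation. No single assumed effect for 1b is needed.

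The cost is wording and, under the second option, slightly lower stated powers. No patients, visits or procedures are added.
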